STUDY PROTOCOL

STUDY TITLE: ISCHEMIC CONDITIONING CHRONIC STROKE STUDY

DATE OF DOCUMENT: 7/26/2019

Research Strategy. This is a prospective, randomized, cross-over study.

Subjects and Recruitment. A total of 15 individuals with chronic stroke (>1 year post-stroke) will be enrolled to complete the aim of this study. Males and females will be recruited equally. Inclusion criteria: Study participants must be between 18-85 years of age, able to give informed consent, >1 year post diagnosis of unilateral cortical or sub-cortical stroke, have residual lower limb paresis. Exclusion criteria: History of blood clots in the extremities or any condition in which compression of the thigh or transient ischemia is contraindicated (e.g. wounds in the leg), chronic pain syndrome, history of head trauma, comorbid neurological disorder, any uncontrolled hypertension (>160/100 mmHg), peripheral vascular disease, a myocardial infarction in the previous year, inability to follow 2 step commands, or history of multiple strokes.

Study participants will be recruited from two sources, a HIPPA compliant database of >40 stroke survivors managed by [name] and a REDCap database managed by [name] which contains the names of >200 individuals with stroke consented to be contacted for research studies. The PI's have successfully used these resources to recruit stroke survivors for previous studies. Participants will be paid \$50 per visit.

General Methods: Study participants will be instructed to fast for 8 hours prior to visiting the adult TRU. A member of the TRU staff will measure height, weight and blood pressure and collect a list of current medications. 10 mL of venous blood will be drawn from an indwelling catheter in the antecubital vein of the non-affected arm into a vacutainer tube with lithium heparin. A total of three blood draws will be performed – at rest, immediately following IC or Sham IC, and immediately following the CPT. The tubes will immediately be centrifuged at 2500 RPM for 15 minutes at 4°C to separate the plasma fraction. The plasma will be transferred to storage vials, frozen in liquid nitrogen, and stored at -80°C until analysis.

IC and IC Sham: IC will be performed in accordance with other studies which have used IC as an intervention¹⁻³ and consistent with our previous work.⁴⁻⁶ Briefly, in supine with legs level with the heart, a rapid inflation cuff (Hokanson SC12 thigh cuff) will be placed around the proximal, paretic thigh and inflated to 225 mmHg for 5 minutes, then released for a 5 minute recovery period. Five cycles of inflation/recovery will be performed. For IC Sham, the cuff will only be inflated to 10 mmHg as participants still perceive the cuff tightness, however the inflation pressure is not high enough to occlude arterial or venous blood flow.

Cold Pressor Test: Water will be cooled to 4-6°C in a bucket and circulated with a sous vide precision cooker. Study participants will submerge their non-affected hand, up to the wrist, into the water for two minutes. Blood pressure and subjective pain will be measured before, during (1 minute) and after the test. Blood will be drawn immediately after the test. Skin temperature will be assessed with a skin thermometer.

Plasma Epinephrine and Norepinephrine Measurements. The concentration of epinephrine and norepinephrine in the plasma samples will be measured by the Physiology Biochemical Analytical Laboratory at MCW using high performance liquid chromatography (HPLC) and established protocols.

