**STATISTICAL ANALYSIS PLAN**

**STUDY TITLE: ISCHEMIC CONDITIONING CHRONIC STROKE STUDY**

**DATE OF DOCUMENT: 7/26/2019**

## **Statistical Design and Analysis**

We will enroll 15 participants in this study based on both the power analysis listed below and a litany of similar studies with enrollments between 10-20 patients. We will compare the absolute change in plasma catecholamines from immediately after IC or IC Sham to immediately after the CPT (i.e. the change in concentration from rest to immediately after the cold pressor test; comparison is  $\Delta IC$  vs.  $\Delta IC$  Sham). Standard deviation of the difference between IC and IC Sham conditions is bounded by 149 pg/ml ( $=\sqrt{2} \times SD$  of  $\Delta$ ) based on a study which examined the changes in norepinephrine levels following the CPT in 15 heart failure patients, where  $SD$  of  $\Delta = 105.55$  pg/ml. Under this conservative assumption, the detectable difference with 80% power ( $\alpha=0.05$ ) is 116 pg/ml with  $n=15$ . A paired t-test will be used to make this comparison. If Shapiro-Wilks test rejects the assumption of normality, we will use exact Wilcoxon signed rank test on non-normally distributed data. Plasma epinephrine concentrations and changes in systolic blood pressure will be compared similarly.

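### Does drawing the post-CPT blood sample from the arm whose hand has just been cooled bias the IC versus Sham comparison?

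*Protocol*

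**What the plan says.** Under General Methods, the protocol takes venous blood "drawn from an indwelling catheter in the antecubital vein of the non-affected arm", with three draws per visit: "at rest, immediately following IC or Sham IC, and immediately following the CPT". Under Cold Pressor Test, participants "submerge their non-affected hand, up to the wrist, into the water for two minutes", and then "Blood will be drawn immediately after the test". The water is circulated at 4-6°C. That section also says: "Blood pressure and subjective pain will be measured before, during (1 minute) and after the test", and "Skin temperature will be assessed with a skin thermometer". It does not name the arm used for blood pressure, the skin temperature site or time, or an interval between the end of immersion and the draw.

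The SAP (Statistical Design and Analysis) takes the change in plasma catecholamines up to the post-CPT sample and compares that change between IC and Sham with a paired test in 15 participants. It adds: "Plasma epinephrine concentrations and changes in systolic blood pressure will be compared similarly". It mentions neither the sampling limb nor skin temperature.

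**The concern.** Subjects and Recruitment requires a unilateral stroke, so the non-affected arm and the non-affected hand belong to the same limb. The antecubital vein lies above the cooled hand. The change score therefore runs from a sample taken before that limb was cooled to one taken straight afterwards. This is so whether the baseline is the resting or the post-IC/Sham sample, because both precede immersion.

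If cooling alters catecholamine levels locally in that limb, each visit's change mixes a whole-body response with a local one. If IC also alters the local part, a difference between IC and Sham could not be put down to whole-body release alone. The protocol gives no reason for using one limb for both purposes and leaves some set-up details open. At stake is the interpretation of the main comparison.

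**Working it through.** **1. The plan's own figure.** Inputs from the SAP: n = 15, SD of a single change 105.55 pg/ml, alpha 0.05, power 80%. Two-sided testing is assumed, since the SAP does not state it.

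- SD of the paired difference: √2 × 105.55 = 149.3, which the SAP gives as 149.
- Standard error: 149/√15 = 38.47. Critical difference: 2.145 × 38.47 = 82.5 pg/ml.
- Noncentral t with 14 degrees of freedom: 80% power at 115.9 pg/ml. The SAP's 116 reproduces. A one-sided test would give 100.6, so two-sided is the right reading.

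**2. What cancels.** Write each visit's change as a whole-body part S plus a local part L. The planned contrast is

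(S_IC + L_IC) − (S_Sham + L_Sham) = (S_IC − S_Sham) + (L_IC − L_Sham).

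If L is the same under both conditions, the second bracket is zero and 116 is unaffected. The protocol fixes the following without distinction between IC and Sham: arm, vein region, immersed hand, water temperature and circulation, depth, two-minute duration, and a draw straight after immersion. What it leaves open is narrower: the exact lag to the draw, the blood pressure arm, and the site and timing of skin temperature. The blood pressure arm has no bearing on a venous concentration.

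**3. How large a differing component would have to be.** The documents give no value, so the values below are assumed, to show scale only. Let b be the mean of L_IC − L_Sham, with no difference in S. Rejection rates for the two-sided paired t-test, n = 15, SD 149:

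| b (pg/ml) | Rejection rate |
|---|---|
| 0 | 5.0% |
| 10 | 5.7% |
| 20 | 7.7% |
| 26.9 | 10% |
| 30 | 11.3% |
| 40 | 16.3% |

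With an assumed within-person correlation of 0.5, the SD of the difference is 105.55 × √(2 × (1 − 0.5)) = 105.55, and 10% is reached at b = 19.1.

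These figures do not measure a fault in this design. A shift of 27/149 = 0.18 SD gives about 10% rejection in any two-sided paired t-test with 15 pairs, whatever its source. They count as false positives only against a null of no difference in whole-body release. The SAP's null is no difference in the change in plasma catecholamines. If IC changes the cooled limb's response, that null is false and rejecting it is correct.

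**4. Noise rather than bias.** Suppose the local part varies between visits regardless of condition, with an assumed SD of 50 pg/ml per visit. The SD of the difference becomes √(2 × (105.55² + 50²)) = 165.2, the detectable difference 128.5, and power at 116 falls to 71.6%. That takes 149 with no within-person correlation, which the SAP presents as a conservative bound. At an assumed correlation of 0.5 the same noise gives √(105.55² + 2 × 50²) = 127.1, still inside 149.

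**The case for a change.** The best case for acting starts from the protocol's own references. One, by its title, reports that IC improves flow-mediated dilatation of an arm artery in chronic stroke survivors. Here IC is applied to the thigh, so an effect of IC on the arm's circulation is not far-fetched, and the cooled arm's local response could differ between IC and Sham. Skin temperature is collected but never used, and a few sentences would fix the draw window, the blood pressure arm and the thermometer site.

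Part of this stands. The shared limb is a fact, no rationale is given, and those details are unstated. The rest does not carry a change:

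- The reference's title says nothing about catecholamines, and nothing in the documents shows a local component or one that differs by condition.
- Comparing skin temperature between conditions would not settle the matter: similar cooling does not prove similar local catecholamine release. With the site unstated, one cannot tell whether the sampled limb is measured at all.
- The SAP already plans a systolic blood pressure comparison, which does not depend on the venous site and can be read beside the catecholamine result.
- Separating the limbs has costs of its own. Access to the affected arm may be harder, that limb may have vascular differences of its own, the blood pressure cuff and the catheter could end up on one arm, and a different immersion site may no longer match the study behind the planning SD, whose sampling limb the SAP does not give.

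**Conclusion.** The observation is correct: the post-CPT sample is drawn from the cooled limb without a stated reason. No bias and no wrong figure follows. The effect on the planned contrast is zero if the local component is equal under IC and Sham, which the common set-up and within-person comparison make the natural working assumption; the documents offer no evidence against it. The 27 pg/ml threshold (19 at an assumed correlation of 0.5) shows only how large an undocumented difference would have to be, and it counts as error only against a claim about whole-body release that neither document makes.

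Using one limb for both purposes is a fair trade-off. The open details are ones a study team can settle in its working procedures and keep the same at both visits. A careful report would describe the endpoint as a venous concentration from the cooled limb and set it beside the systolic blood pressure result. That is a matter of reporting and needs no change to the plan. The cancellation covers only the IC versus Sham comparison: the CPT response within a single visit would still contain any local component.

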**STATISTICAL ANALYSIS PLAN**

**STUDY TITLE: ISCHEMIC CONDITIONING CHRONIC STROKE STUDY**

**DATE OF DOCUMENT: 7/26/2019**

## **Statistical Design and Analysis**

We will enroll 15 participants in this study based on both the power analysis listed below and a litany of similar studies with enrollments between 10-20 patients. We will compare the absolute change in plasma catecholamines from immediately after IC or IC Sham to immediately after the CPT (i.e. the change in concentration from rest to immediately after the cold pressor test; comparison is  $\Delta IC$  vs.  $\Delta IC$  Sham). Standard deviation of the difference between IC and IC Sham conditions is bounded by 149 pg/ml ( $=\sqrt{2} \times SD$  of  $\Delta$ ) based on a study which examined the changes in norepinephrine levels following the CPT in 15 heart failure patients, where  $SD$  of  $\Delta = 105.55$  pg/ml. Under this conservative assumption, the detectable difference with 80% power ( $\alpha=0.05$ ) is 116 pg/ml with  $n=15$ . A paired t-test will be used to make this comparison. If Shapiro-Wilks test rejects the assumption of normality, we will use exact Wilcoxon signed rank test on non-normally distributed data. Plasma epinephrine concentrations and changes in systolic blood pressure will be compared similarly.

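### Does enrolling exactly 15 people, with no rule for replacing incomplete cross-over pairs, undermine the stated 80% power?

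*SAP*

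**What the plan says.** The protocol's Research Strategy reads "This is a prospective, randomized, cross-over study". Under Subjects and Recruitment, "A total of 15 individuals with chronic stroke (>1 year post-stroke) will be enrolled to complete the aim of this study". Under General Methods, "A total of three blood draws will be performed": at rest, after IC or sham, and after the cold pressor test (CPT).

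The SAP's single section, Statistical Design and Analysis, opens with "We will enroll 15 participants in this study based on both the power analysis listed below" and adds a second basis, similar studies that enrolled 10 to 20 patients. It takes 149 pg/ml as an upper bound for the SD of the IC-minus-sham difference and calls this assumption conservative. It then gives "the detectable difference with 80% power" as 116 pg/ml at n=15 and α=0.05. On the test: "A paired t-test will be used to make this comparison". An exact signed-rank test is the fallback if normality is rejected. Epinephrine and systolic blood pressure are to be handled in the same way.

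Neither document mentions withdrawal, missed visits, unusable samples or replacement.

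**The concern.** The SD in the power calculation is that of a within-person difference, so n=15 means 15 people with a usable change under both conditions. For norepinephrine that takes four good plasma results per person, two in each session. Enrolment is also 15, so there is no slack in the count. One missed visit, failed catheter or spoiled tube removes a whole pair, and the stated power no longer applies exactly.

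There is also a question of conduct. With no written rule, the choice between replacing someone and analysing fewer pairs could be made after results are known. In a trial of 15, one person can matter.

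**Working it through.** **Inputs from the SAP.** SD of Δ = 105.55 pg/ml; n = 15; α = 0.05; power 80%; detectable difference 116 pg/ml. Sidedness is not stated. Two-sided reproduces the figure; one-sided gives about 101 pg/ml and does not.

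**Step 1: the SAP's own figure.** SD of the paired difference = √2 × 105.55 = 149.27. Power of a paired t-test is P(T > t₀.₉₇₅,ₙ₋₁), with T noncentral t on n−1 degrees of freedom and noncentrality 116 × √n / SD; the opposite tail is negligible. For n = 15 the noncentrality is 116 × √15 / 149.27 = 3.01 and power is 79.9%. The difference with exactly 80% power is 116.1 pg/ml. The SAP's 116 is confirmed.

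**Step 2: fewer complete pairs at the same SD.**

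| Complete pairs | Power for 116 pg/ml | Difference detectable with 80% power |
|---|---|---|
| 15 | 79.9% | 116.1 |
| 14 | 76.7% | 120.9 |
| 13 | 73.0% | 126.4 |
| 12 | 68.9% | 132.6 |

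**Step 3: how likely is a loss?** The documents give no completion rate, so these are assumptions. If each person independently gives a complete pair with probability 0.95, 0.90 or 0.80, all 15 are complete with probability 0.95¹⁵ = 46%, 0.90¹⁵ = 21% or 0.80¹⁵ = 4%. Averaging Step 2 power over the binomial number of pairs gives 77%, 75% or 68%.

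**Step 4: what the SD bound holds in reserve.** With equal variances and within-person correlation ρ between the two changes, the SD of the difference is 105.55 × √(2(1−ρ)). The SAP's 149 is ρ = 0. The documents give no ρ, so these too are assumptions.

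| ρ | SD | 15 pairs | 14 | 13 | 12 |
|---|---|---|---|---|---|
| 0 | 149.3 | 80% | 77% | 73% | 69% |
| 0.3 | 124.9 | 92% | 89% | 87% | 83% |
| 0.5 | 105.6 | 98% | 97% | 95% | 93% |

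The correlation that restores the 15-pair power of Step 1 is 0.08 with 14 pairs, 0.16 with 13 and 0.23 with 12.

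**Step 5: what the analysis does with an incomplete pair.** Both the paired t-test and the signed-rank test work on within-person differences, so someone without both changes contributes nothing. The analysis set follows from the choice of test. If pairs are lost, the same test runs on fewer differences, with its type I error unaffected by the smaller count.

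**The case for a change.** The strongest case for a change is that the reserve in Step 4 is not established. No correlation is stated, and the 105.55 comes from heart failure patients, so calling the SD conservative speaks to the correlation and not to whether that SD carries over to chronic stroke. At an assumed ρ of 0.2 with 80% completion, average power is 77%, still below target. A correlation, whatever its size, also does not say who decides on replacement, or when. A short rule would be cheap: holding 15 complete pairs means enrolling 15/0.95 = 15.8, 15/0.90 = 16.7 or 15/0.80 = 18.8 people on average, and the protocol cites a database of more than 200 "individuals with stroke consented to be contacted for research studies".

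Part of this stands. The documents are silent on replacement, and a sentence on it would do no harm. But 116 pg/ml is reported as what 15 pairs can detect, not as a clinically chosen target, so a move to 121 or 126 crosses no threshold in the plan. Twelve to 14 pairs also stay within the 10 to 20 that the SAP gives as its second basis. Epinephrine and blood pressure have no power statement to lose.

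A replacement rule has costs of its own. Replacing until 15 are complete restores the count but does nothing about losses related to the condition, such as intolerance of the cuff. A definition of completeness based on plasma samples does not fit blood pressure. It would also first need the SAP's two descriptions of the starting point of Δ (after IC or sham, and at rest) to be reconciled, which is a separate matter.

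**Conclusion.** No change follows. The SAP's power figure is correct for what it states: 15 pairs at an SD of 149 pg/ml. The exposure is about 3 percentage points of power for one lost pair and 11 for three (79.9 − 76.7 = 3.2; 79.9 − 68.9 = 11.0), and only if the correlation is zero; a correlation of 0.08 to 0.23 cancels it. This rests on the SAP's SD for Δ applying in this population and on the correlation not being negative.

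The gap is one that analysts fill sensibly: analyse the complete pairs for each outcome, report everyone randomised with the reason for any missing pair, and read the detectable difference as 121, 126 or 133 pg/ml if 14, 13 or 12 pairs remain. If the team prefers to replace people, the recruitment pool allows it, and the power figure, SD and test stay as they are. Either course gives a valid comparison.

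### Order is randomized but unused in the analysis: with an 8:7 blocked list, adjusting for it costs about 1 pg/ml and gains power once the cold pressor response differs between visits by more than about 21 pg/ml

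*SAP*

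**What the plan says.** The Protocol (Research Strategy) gives the design in one line: "This is a prospective, randomized, cross-over study". Every participant receives both conditions, so order is the only thing left to randomize. That is an inference, because neither document describes how order is allocated or whether it is balanced.

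The Protocol (Cold Pressor Test) describes one cold challenge, with no difference between conditions: "Study participants will submerge their non-affected hand, up to the wrist, into the water for two minutes".

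The SAP (Statistical Design and Analysis) compares the change in plasma catecholamines under IC with the change under Sham: "A paired t-test will be used to make this comparison". Its fallback is conditional ("If Shapiro-Wilks test rejects the assumption of normality"), and in that case "we will use exact Wilcoxon signed rank test on non-normally distributed data". Neither branch has an order or period term. Secondary measures follow the same route: "Plasma epinephrine concentrations and changes in systolic blood pressure will be compared similarly".

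The power statement rests on an upper limit for variability: "Standard deviation of the difference between IC and IC Sham conditions is bounded by 149 pg/ml". From this the SAP derives a detectable difference of 116 pg/ml with 15 participants.

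**The concern.** Each participant meets the same cold stressor twice, so the mean response may differ between visits. A visit shift in catecholamine level does no harm, because the endpoint is a change within a visit and the shift cancels. A visit difference P in the response itself does not cancel. It adds +P to the IC-minus-Sham difference when IC comes second and −P when IC comes first.

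The paired t-test leaves this in the error variance and, if the orders are unequal in number, in the estimate as well. Type I error is not inflated, but power falls. The order information that would remove P is already generated by the randomization and then discarded. In a trial of 15 with no stated allowance for dropout, that power is worth protecting if it costs little.

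**Working it through.** **Inputs.** From the SAP: n = 15, SD of the change 105.55 pg/ml, SD of the paired difference √2 × 105.55 = 149.27, α = 0.05 (two-sided reproduces the SAP's figure), effect 116 pg/ml. Assumed: 8:7 order split, all participants complete, no carryover, P from 0 to 100 pg/ml. P of 25, 50 and 100 is 0.24, 0.47 and 0.95 of the SAP's SD of change.

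**The SAP's own figure.** Paired t, 14 df, SE = 149.27/√15 = 38.54. The noncentral t gives a detectable difference of 116.1 pg/ml (115.9 with SD rounded to 149). The stated 116 is reproduced.

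**Order-adjusted test.** The estimate is the mean of the two order-specific mean differences, so P drops out. SE = (149.27/2) × √(1/8 + 1/7) = 74.635 × 0.5175 = 38.63, on 13 df. The detectable difference is 117.1 pg/ml, a cost of 117.1 − 116.1 = 1.0. Power at 116 is 79.3% against 79.9%.

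**Paired t-test when P is not zero.** The estimate shifts by ±P × (8 − 7)/15 = ±P/15. The sum of squares becomes noncentral chi-square with noncentrality 4 × 8 × 7 × P²/(15 × 149.27²), which is 1.68 at P = 50 and 6.70 at P = 100. Numerical integration at effect 116 and 8:7 gives the following, where toward and away say whether P moves the estimate toward or away from the effect:

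| P (pg/ml) | Paired, toward | Paired, away | Paired, mean | Adjusted |
|---|---|---|---|---|
| 0 | 79.9% | 79.9% | 79.9% | 79.3% |
| 25 | 80% | 78% | 79.0% | 79.3% |
| 50 | 79% | 74% | 76.3% | 79.3% |
| 100 | 71% | 60% | 65.5% | 79.3% |

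Simulation with 200,000 trials per cell agrees (P = 100, toward: paired 71.2%, adjusted 79.1%). Setting the two powers equal gives a break-even P of 21.3 pg/ml averaged over sign (11 if away, 44 if toward). Paired type I error at P of 0, 50 and 100 is 5.0%, 4.0% and 2.1%.

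**Smaller SD.** With within-person correlation r, SD = 105.55 × √(2(1 − r)):

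| r | SD | Paired, P = 50 (toward / away) | Paired, P = 100 (toward / away) | Adjusted |
|---|---|---|---|---|
| 0.2 | 133.5 | 87% / 82% | 79% / 68% | 87.3% |
| 0.3 | 124.9 | 90% / 87% | 83% / 72% | 91.2% |
| 0.5 | 105.55 | 97% / 95% | 92% / 83% | 97.5% |

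Break-even at SD 105.55 is about 17 pg/ml.

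**If order is not balanced.** At SD 149.27 the adjusted detectable difference is 119 pg/ml (power 77.8%) at 9:6 and 124 (74.7%) at 10:5. Averaged over Binomial(15, 0.5) splits, adjusted power is 76.4%. Paired power is 79.9%, 78.8%, 75.6% and 64.1% at P of 0, 25, 50 and 100. Break-even rises to about 45 pg/ml (36 at SD 105.55).

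**The case against.** The strongest reply is that nothing is broken. The paired t-test is valid, the 116 pg/ml reproduces, and the gain depends on a quantity that neither document gives. At the bounding SD the average gain is 0.3 points at P = 25 and 3 points at P = 50. The large gains need P near 100, close to the treatment effect itself. The SAP also calls its SD conservative. Averaged over the sign of P, the planned test keeps at least 80% power until P is about 52 at r = 0.1, 75 at 0.2, 92 at 0.3 and 121 at 0.5. Read literally, the bound on the paired SD could even include a visit contribution, although its √2 derivation does not address one. And without blocked order, which the Protocol does not specify, the adjustment can lose power.

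Most of this stands as a limit on the size of the gain. The 21 pg/ml threshold is also not a constant. At SD 149 it is about 16 for an effect of 60 and 24 for an effect of 160, besides depending on the sign of P.

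It does not remove the point. A smaller SD raises the power of both tests, and the break-even P falls slightly rather than disappearing. The trade is also uneven: 0.6 points lost if P is zero, against 8 to 20 points gained at P = 100 and the bounding SD. The objection about unblocked order is right, which is why the two edits belong together.

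One gap remains: the signed-rank fallback would still ignore order. At 8:7 and SD 149.27 its simulated power is 78% at P = 0, 76% / 71% at P = 50 and 68% / 56% at P = 100 (toward / away).

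**Conclusion.** The concern holds as an efficiency improvement, not as a validity error. With order blocked to 8:7, adjusting for it costs about 1 pg/ml in detectable difference. It holds power at 79.3% whatever P is and removes the P/15 shift in the estimate. It is the better test once P exceeds about 21 pg/ml.

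These figures assume an effect of 116 pg/ml, SD 149, 15 completers, no carryover and averaging over the sign of P. The true P is unknown, so how much will be gained cannot be stated. At an SD near 105 the practical loss from the planned test is small until P is large. No calculation was made for epinephrine or systolic blood pressure.

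**What to change.** **SAP, Statistical Design and Analysis.** Replace the paired t-test sentence with: *The IC-minus-Sham difference in each participant's change will be regressed on a ±1 order indicator (IC first or Sham first), and the treatment effect tested as the intercept on n − 2 df (13 df with 15 complete participants).* Use the same model for epinephrine and systolic blood pressure, and restate the detectable difference as 117 pg/ml.

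Apply the normality test to the residuals of this regression. This is for consistency and will rarely change the branch: on raw differences the test rejects in only 4.5% of simulated trials at P = 100 and SD 149.27. Keep the signed-rank fallback as written. A rank-sum version that uses order is optional and loses power at small P.

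**Protocol, Research Strategy.** State that order is randomized in blocks giving 8:7. If order cannot be balanced, keeping the paired t-test is reasonable unless P above about 45 pg/ml is expected.

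State the regression directly rather than a mixed model with a random participant effect. That model matches the 13-df test only when the participant variance estimate is positive, and at zero correlation the estimate is zero in about half of trials. The order term does not address carryover.

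**Cost.** Two sentences, a blocked list and one degree of freedom. Dropout adds a little. Adjusted against paired, the detectable differences are 121.8 vs 120.9 pg/ml (7:7), 123.0 vs 120.9 (8:6), 127.8 vs 126.4 (7:6) and 131.0 vs 126.4 (8:5). The adjustment therefore adds about 1 to 5 pg/ml on top of the lost participants.
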